7.5 Data analysis

7.5.1 Context and rationale for analysis plan

Analytic Population

Primary analyses will be conducted in the real-world study population based on the first study treatment initiated. This approach is intended to emulate the intent-to-treat analysis conducted in the PALOMA-2 trial, where patients were analyzed based on their randomized treatment assignment. As crossover between treatment arms was not allowed in the PALOMA-2 trial, intent-to-treat and per-protocol trial analyses would produce equivalent results. Conversely, real-world patients initially prescribed letrozole could initiate palbociclib after the end of the exposure ascertainment window. To investigate the potential for crossover between comparison groups prior to disease progression in the real-world population, descriptive analyses of all first-line treatments initiated and time between treatments will be conducted.

IPTW will be used to approximate full conditional exchangeability between the comparison groups and facilitate estimation of the population average treatment effect.¹⁶⁻¹⁸ Propensity scores (PS) reflecting the conditional probability of initiating treatment with palbociclib and letrozole will be calculated via multivariable logistic regression. Exposure to palbociclib and letrozole will be regressed on *a priori* identified potential confounders ([Table 9](#)). Inverse probability of treatment weights will be calculated as the inverse of the propensity score (1/PS) for patients in the exposed group and as the inverse of one minus the propensity score (1/1-PS) for comparator patients.¹⁹ Patients are therefore weighted by the inverse probability of initiating the treatment they actually started, conditional on the observed covariates included as independent variables in the PS model. This approach aims to create a pseudo-population with full exchangeability on measured confounders within which the treatment effect is estimated.

Confounder balance will be assessed by comparing the absolute standardized difference (ASD) in the distribution of categorical variable levels and the mean of continuous variables between the weighted exposure groups.¹⁶ If balance is not achieved (ASD > 0.1), alternative specifications of the PS model, e.g., including variable transformations and interaction terms, will be explored. Confounders with insufficient balance may also be included as covariates in the outcome models.

The distribution of baseline patient demographic and clinical characteristics will be compared between comparator patients who index before 2015 and on/after 2015 to understand if differences exist between those who received the comparator treatments before and after palbociclib approval in this indication. Characteristics to be compared are described in [Table 9](#). Differences will be assessed using t-tests, chi squared tests, and accompanying 95% confidence intervals.

Descriptive Analyses

The distribution of patient baseline demographic and clinical characteristics will be compared between the unweighted and weighted real-world populations and the PALOMA-2 trial population. Characteristics to be compared are described in [Table 9](#). Differences will be assessed using t-tests, chi squared tests, and accompanying 95% confidence intervals.

Reasons for exclusion and censoring will be presented in a Consolidated Standards of Reporting Trials (CONSORT) diagram and distributions of missingness of inclusion/exclusion criteria and potential confounders will be calculated and compared by exposure group.²⁰

Treatment Effectiveness

Similar to the PALOMA-2 trial, comparative treatment effectiveness of palbociclib and letrozole versus letrozole alone will be estimated using median rwPFS and by comparing the hazards of progression and death in the two exposure groups. Follow-up will be administratively censored at 33 months to emulate maximum follow-up in the PALOMA-2 trial at the time that results were reported.² We will emulate subgroup analyses performed in the trial, except where sample size is less than 10 in each exposure group. Post-hoc analyses to explore effect modification will be conducted for characteristics where distributions differ between the trial and RW populations.

Details of the analytic approach are presented in [Table 10](#).

Table 10. Primary and subgroup analysis specification

Hypothesis:	Median rwPFS is longer and the hazard of progression is lower among patients who initiated palbociclib and letrozole versus letrozole alone.
Exposure contrast:	Patients initiating palbociclib and letrozole compared with patients initiating letrozole alone in the first line metastatic setting.
Outcome:	rwPFS
Analytic software:	Aetion Substantiate Version 5.01 (or latest version)
Model(s):	
Median rwPFS will be estimated using a Kaplan-Meier estimator, weighted by time-fixed inverse probability of treatment weights. The weighted survival probability $S_a(t)$ for exposure group 'A=a' at time 't' will be as follows:
 $S_a(t) = \prod_t 1 - \frac{d_{ta}}{r_{ta}}$ 
where $d_{ta} = \sum_{i=1}^N w_{it} \cdot Y_{it} \cdot I(A_{it} = a)$ denotes the weighted number of events and $r_{ta} = \sum_{i=1}^N w_{it} \cdot I(A_{it} = a)$ denotes the weighted risk set.²¹⁻²³ This is equivalent to calculating the Kaplan-Meier estimator in the IPTW weighted population.²² A non-parametric bootstrap will be used to derive 95% confidence intervals.
 
A Cox proportional hazards model will be used to estimate the hazard ratio at 33 months in the IPTW weighted population as follows:
 $h(t, L_0) = h_0(t) * e^{\beta_1 A_0 + \beta_2^T L_0}$

	
where $h(t, L_0)$ is the hazard of progression at discrete time interval 't' conditional on the vector of potential confounders ' L_0' assessed at baseline; $h_0(t)$ is the baseline hazard at discrete time interval 't'; and A_0 is an indicator for treatment initiation, coded as '1' and '0' for the exposure and comparator group, respectively. Patients with an outcome or censoring event on Day 0 will be assigned a follow-up time of 0.5 days. The proportional hazards assumption will be checked using plots that display the scaled Schoenfeld residuals vs. time for each covariate; if violations are detected, a time-dependent or stratified Cox proportional hazards model will be considered. The Efron method of handling ties will be used.


Confounding adjustment method
	
Time-fixed inverse probability of treatment weights will be used to adjust for confounding. Individual-level weights will be estimated by the following formula:
 $W^A = \frac{1}{f(A L_0)}$ 
where A is the first study treatment that the patient initiated and L_0 is a vector of baseline confounders.
 
The quantity in the denominator $f(A L_0)$—the probability of exposure to treatment A given baseline confounders L_0—will be estimated using a logistic regression model with A as the dependent variable and the vector L_0 as the independent variables. The distribution of weights will be used to identify potential extreme weights. If extreme weights are identified, weight truncation and/or stabilization will be considered.
 
All potential confounder variables will be considered for inclusion in the weight estimation (Table 9). However, as it is not possible to predict the quantity of missing values and sparseness of the data at the time of writing this protocol, the precise functional form of the final regression model will be determined at the time of analysis. Thus, variables with high missingness will be excluded from the final model. Additionally, categorical variables may be collapsed to ensure convergence of the propensity score model.

Missing data methods
	
Data missingness was assessed as part of an initial feasibility assessment (Appendix B); therefore, key variables are expected to have a high degree of completeness. If substantial missingness results in an insufficient sample size for the complete analytic dataset, alternative variable specifications (e.g., changing the time frames over which variables are assessed) or exclusion of variables may be considered.

Subgroup Analyses
	
Cox proportional hazards models will be assessed in the following subgroups to align with the trial, as feasible. Measurable disease, international region, and histopathological classification were included as subgroups in the trial but cannot be emulated in the RWD source.
 
 1. Age (18 to <65 yrs, ≥65 yrs) 2. Race (White, Asian) 3. Site of metastatic disease at baseline (visceral (lung, liver), non-visceral) 4. Disease-free interval (<12 months, ≥12 months, de novo metastatic)

	
 5. Prior hormonal therapy (yes, no) 6. Performance status (ECOG 0 or Karnofsky Score 100, ECOG 1-2 or Karnofsky Score 50-90) 7. Bone-only disease at baseline (yes, no) 8. Prior chemotherapy (yes, no) 9. Most recent therapy (aromatase inhibitor, antiestrogen) 10. Number of disease sites (1, ≥2)
--	---

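### Table 10 writes the primary weighted Cox model with the full confounder vector, while the text of Section 7.5.1 targets a population-average effect and makes such covariates optional; the plan should settle which hazard ratio is primary

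*Combined protocol and SAP*

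**What the plan says.** The text of Section 7.5.1 says the weights are there to "facilitate estimation of the population average treatment effect". Balance is judged by the absolute standardised difference (ASD): "If balance is not achieved (ASD > 0.1), alternative specifications of the PS model" will be explored. The next step is optional: "Confounders with insufficient balance may also be included as covariates in the outcome models".

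Table 10, Model(s), gives one Cox model, fitted in the weighted population. Its linear predictor is b1·A0 + b2'·L0, and its hazard is described as "conditional on the vector of potential confounders". Proportional hazards are checked with "scaled Schoenfeld residuals vs. time for each covariate". The Kaplan-Meier estimator in the same cell carries weights only, with no L0: "This is equivalent to calculating the Kaplan-Meier estimator in the IPTW weighted population".

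Table 10, Confounding adjustment method, uses the same symbol for the propensity model, where "L_0 is a vector of baseline confounders". It names only the weights as the method: "Time-fixed inverse probability of treatment weights will be used to adjust for confounding".

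Table 2 makes the hazard ratio the main measure of effect. No section labels it marginal or conditional.

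**The concern.** The text describes a weighted model with treatment alone, plus leftover confounders if needed. The formula describes a weighted model with every confounder, always. Two competent analysts could fit different primary models and both claim to follow the plan.

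The two models do not estimate the same quantity. The hazard ratio is non-collapsible: even with perfect balance, conditioning on prognostic covariates moves it away from 1. Read literally, the headline hazard ratio and the medians reported beside it would be on different scales.

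Section 5 judges agreement with the trial on direction and on closeness in size, with no numerical threshold. Non-collapsibility acts on size, which is the part left to judgement. If the model is not fixed beforehand, the choice between two hazard ratios could be made after both have been seen.

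**Working it through.** **1. The plan's own figures.** Table 13 supplies 0.58 (trial hazard ratio), 0.72 (its upper limit) and 57.7% (event prevalence in the unexposed). With N = (1.960 + z_power)² / [0.25 · (ln HR)² · 0.577], the row for 0.58 at 80% power is 7.85 / (0.25 × 0.2967 × 0.577) = 183.4, rounded up to 184 as printed. The other five rows (530, 396, 675, 505, 246) also reproduce. No arithmetic in the plan is in dispute. Table 13 labels the 57.7% as deaths; I take it as the control event fraction for progression or death, which is an assumption.

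**2. Size of the conditional-marginal gap.** Assume exponential times, hazard λ·exp(b·A + L) with L normal (mean 0, SD s), perfect balance, and administrative censoring only. The marginal survival curve is S_a(t) = E[exp(−λt·exp(b·a + L))]. Choose λ so that control events equal the stated fraction. The marginal log hazard ratio β solves the large-sample Cox score equation

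∫ { f1 − (f1 + f0) · S1·e^β / (S1·e^β + S0) } dt = 0.

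Then find the b for which e^β = 0.58. The values of s are assumptions.

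| SD of L | Conditional HR, 57.7% events | Log shift | Conditional HR, 45% to 80% events | Shift in SEs, n = 1,604 | Shift in SEs, n = 800 |
|---|---|---|---|---|---|
| 0.25 | 0.574 | 0.010 | 0.576 to 0.570 | 0.14 | 0.10 |
| 0.5 | 0.557 | 0.041 | 0.563 to 0.544 | 0.56 | 0.40 |
| 0.75 | 0.529 | 0.092 | 0.541 to 0.506 | 1.26 | 0.89 |
| 1.0 | 0.495 | 0.158 | 0.512 to 0.463 | 2.17 | 1.53 |

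The SE uses the Section 7.9 feasibility counts, 944 + 660 = 1,604. Control events are 660 × 0.577 = 381. Exposed events are 944 × (1 − 0.423^0.58) = 371. So SE = √(1/381 + 1/371) = 0.073. For an assumed 800 patients after attrition it is 0.073 × √(1604/800) = 0.103. Weighting enlarges the SE, so the last two columns are upper values.

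By log symmetry the trial's lower limit is about 0.58²/0.72 = 0.467. At 57.7% events even 0.495 lies inside that interval. Only the extreme corner (SD 1.0, 80% events, 0.463) falls just outside.

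**3. Could the optional clause matter?** Year of initiation is a Table 9 covariate, entry starts in February 2010 (Section 7.3.1), and Table 11 ties accelerated approval to February 2015. If nobody is exposed before 2015 (an inference) and years are kept separate, each earlier comparator has weight 1/(1 − 0) = 1. With p = n_pre/1,604, the ASD of a pre-2015 indicator is p / √(p(1 − p)/2) = √(2p/(1 − p)). Eight such patients give 0.1001. If 25% (165) or 50% (330) of the 660 comparators are pre-2015 (assumed), it is 0.48 or 0.72.

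**4. Which specification recovers the marginal 0.58?** Simulation: 3 × 150,000 patients per scenario, 944:660 split, logistic propensity model with categorical year, weights as in the plan, half of comparators pre-2015, and pre-2015 hazard 1.25 or 0.8 times the later hazard (share and factors assumed). Monte Carlo SE is about 0.003. Entries are for SD 0.25 / 0.5 / 0.75 / 1.0.

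| Weighted model | Pre-2015 hazard × 1.25 | Pre-2015 hazard × 0.8 |
|---|---|---|
| Treatment only | 0.555 / 0.558 / 0.562 / 0.561 | 0.612 / 0.601 / 0.600 / 0.603 |
| Treatment + year (the unbalanced confounder) | 0.580 / 0.583 / 0.584 / 0.581 | 0.586 / 0.576 / 0.578 / 0.584 |
| Treatment + full L0 | 0.574 / 0.559 / 0.532 / 0.495 | 0.580 / 0.553 / 0.527 / 0.499 |

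A separate run of this kind gave 0.554 to 0.606, 0.575 to 0.582 and 0.499 to 0.572 for the three models. The full-L0 model tracks its own conditional target, so its distance from 0.58 is non-collapsibility and not bias.

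**The case against.** The literal reading rests on one formula and its gloss. The abstract, Section 7.1.2, Section 8 and Table 10 itself name only weighting as the control for confounding. The formula is compatible with a general form whose b2 term is used only when imbalance remains. The residual check per covariate is weak evidence, because treatment is itself a Cox covariate. The population-average wording may be meant to separate all patients from the treated only, not marginal from conditional. All of this is fair, and the milder reading may be the intended one. But the plan never states it. The sentence leaving the functional form open concerns the weight model, so it does not settle the matter.

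A weighted Cox model that also adjusts for covariates is not invalid, and nothing here says it is. Nor can the documents show that a conditional hazard ratio is the wrong comparator for 0.58. Section 7.1.1 says only that the trial used a Cox model, so treating 0.58 as marginal is an assumption.

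A reader might infer that the optional clause is bound to be triggered by year of initiation. The documents do not support that. Table 10 allows categories to be merged so that the propensity model converges, and years with no exposed patients are a natural case. In a run with pre-2015 merged into 2015-2016, the merged level had an ASD of about 0.002, so a check on modelled levels would pass. The underlying pre-2015 indicator still had an ASD of about 0.97. The clause may be triggered, if nobody is exposed before 2015 and years are not merged.

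A reader might also infer that the cure is a bare treatment-only model. With year unbalanced, it is no better than full L0 at SD 0.5 or below. With merged years it moved further from 0.58, to 0.539-0.555 or 0.615-0.629. That part of the objection stands and shapes the fix.

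**Conclusion.** The inconsistency is real and should be resolved before analysis. Table 10 and the text of Section 7.5.1 specify different primary models, and the text does not say which governs. It does not threaten the study's direction of effect. The gap is small if the prognostic-score SD is 0.5 or below, at most 0.56 of an unweighted SE at 1,604 patients and 57.7% events. It becomes material to a judgement about size at 0.75 to 1.0. These figures rest on assumed prognostic strength, exponential times, 57.7% as the control event fraction, and a marginal trial hazard ratio of 0.58. The finding that the models differ in target rests on the text alone.

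**What to change.** In Table 10, write the primary weighted model as h0(t)·exp(b1·A0). Add only those confounders whose ASD stays above 0.1 after the propensity model has been re-specified. This turns the option in Section 7.5.1 into a rule. If years are merged, check the ASD of a pre-2015 indicator as well.

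State before analysis that this model gives the headline hazard ratio. Label it marginal if no covariate is added; otherwise label it conditional on the named covariates, or standardise it to a marginal value. Keep the full-L0 model as a sensitivity analysis labelled conditional.

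If full L0 is what the authors intend as primary, say so in the text of Section 7.5.1 and standardise the hazard ratio before setting it against 0.58.

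The cost is a formula edit and a few sentences, with no new data. The downside is less covariate protection against small residual imbalance than full L0 gives; the retained sensitivity analysis covers that. The contemporaneous cohort already planned in Table 11 remains a second check on the calendar-year problem.

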7.5.2 Context and rationale for sensitivity analyses

Sensitivity analyses will be conducted to explore the potential impact of several key study design elements. Planned analyses and their respective goals are presented in [Table 11](#).

Table 11. Sensitivity analyses – rationale, strengths and limitations

Description	Primary Analysis	Sensitivity Analysis	Rationale	Strengths of the sensitivity analysis compared to the primary	Limitations of the sensitivity analysis compared to the primary
Contemporaneous cohort	Study population includes patients with first study drug initiation from February 1, 2010 to June 20, 2023.	The study population will be restricted to patients with first study drug initiation from February 1, 2015 to June 20, 2023 to coincide with Food and Drug Administration (FDA) accelerated approval of palbociclib.	Removing historical comparator patients will decrease potential confounding due to changes in treatment paradigms over time.	This analysis will provide effect estimates using a control group that more closely resembles the exposed group with respect to treatment standards.	Restriction to contemporaneous comparator patients may reduce the sample size and introduce other unmeasured sources of confounding due to differences between patients who do and do not initiate newly available treatment.

Description	Primary Analysis	Sensitivity Analysis	Rationale	Strengths of the sensitivity analysis compared to the primary	Limitations of the sensitivity analysis compared to the primary
Limit eligible cohort entry dates to six months prior to the end of the data	Eligible cohort entry period limited to dates at least one month prior to the end of the data.	The eligible cohort entry period will be limited to dates at least six months before the end of the data (February 1, 2010 to February 20, 2023).	Patients identified toward the end of the available study period may not have adjudicated death data, leading to underestimates of death.	Greater minimum follow-up time and opportunity for death to be identified.	The sample size will be reduced relative to the primary analysis.
Modified exposure ascertainment window (one day)	Exposure status is ascertained over a 15-day window following first study drug initiation.	The exposure ascertainment window will be shortened to occur over a single day.	Shortening the exposure ascertainment window will exclude patients who initiate letrozole and palbociclib greater than 1 day apart from the exposed group.	This analysis will more closely align the treatment strategy in the exposed group to that of the trial.	Patients who initiate palbociclib greater than 1 day after letrozole will be eligible for inclusion in the comparator group, which may bias results towards the null.
Modified exposure ascertainment window (30 days)	Exposure status is ascertained over a 15-day window following first study drug initiation.	The exposure ascertainment window will be increased to occur over 30 days.	Increasing the exposure ascertainment window will include patients who initiate letrozole and palbociclib greater than 15 days apart in the exposed group.	This analysis will increase follow-up time for patients who initiate study drugs further apart in time and will employ a more flexible definition of the exposure ascertainment period that aligns with the data vendor line of therapy definition.	Patients who initiate palbociclib greater than 15 days after letrozole will be eligible for inclusion in the exposed group, which may less accurately reflect the treatment strategy used in the trial.

Description	Primary Analysis	Sensitivity Analysis	Rationale	Strengths of the sensitivity analysis compared to the primary	Limitations of the sensitivity analysis compared to the primary
Loss to follow-up censoring definition	Patients are censored on the last date prior to a period of >90 days without curated EHR activity and without death.	Censor patients on the last date prior to a period of >180 days without curated EHR activity and without death.	Lengthening the time period without curated EHR activity will allow patients who are using healthcare less frequently to have outcomes recorded after a gap in 180 days of activity.	Progression and death events that occur after a gap of 90 days without curated EHR activity will be included.	Lengthening the time period without curated EHR activity will increase the possibility of unobserved events or censoring reasons and potentially overestimate rwPFS.
ECOG performance status assessment window	ECOG performance status for study inclusion will be assessed within 90 days from first study treatment initiation.	ECOG performance status for study inclusion will be assessed within 30 days from first study treatment initiation.	Shortening the assessment window for ECOG performance status may more accurately reflect patients' status at the time of study treatment initiation and will provide information on the sensitivity of results to this key inclusion criteria.	Assessing ECOG status closer in time to study treatment initiation may create a study population that is more similar to the trial population.	A larger number of patients may be missing ECOG performance status during the shorter time period. Patients with missing values will be included in the analysis in line with the primary approach.
Complete case - ECOG performance status	Patients with missing ECOG or Karnofsky performance status in the 90 days prior to first study treatment initiation are included.	Patients with missing ECOG or Karnofsky performance status in the 90 days prior to first study treatment initiation will be excluded.	Removing patients with missing ECOG performance status may reduce misclassification of disease severity and will enable descriptive comparison of the study population with and without these patients.	Excluding patients with missing ECOG may create a study population that is more similar to the trial population.	The sample size will be reduced.

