7.3 Setting

7.3.1 Context and rationale for definition of Time 0 (and other primary time anchors) for entry to the study population

Figure 2 displays the study design diagram for the primary analysis. Candidate exposed and comparator patients will be identified as those initiating treatment for metastatic disease with palbociclib and/or letrozole. Study exposure group will be ascertained within a 15-day time

window (i.e., 'exposure ascertainment window'), beginning on the day of the first record of a study drug (palbociclib or letrozole) (Day -15), and ending 15 days later on Day -1. Patients experiencing an outcome or censoring event during this window will be excluded. Additional information on the exposure ascertainment window is provided in [Section 7.4.1](#). Follow-up for progression and death will begin on Day 0 ('Time 0'). To avoid immortal time bias, Time 0 will occur after the exposure ascertainment window for all patients, irrespective of exposure status. The operational definition of Time 0 is provided in [Table 3](#). The date of first study drug initiation will be restricted to dates from February 1, 2010 to June 20, 2023 to reflect current treatment paradigms at the time of the PALOMA-2 trial, and to allow a minimum available follow-up time of one month prior to the end of data for all patients, respectively. It should be noted that the first line of metastatic treatment can be initiated up to 30 days before the documented date of metastatic diagnosis per the data vendor's line of therapy definitions.

Table 3. Operational definition of Time 0

Study population name(s)	Time Anchor Description	Type of entry	Washout window	Incident with respect to...
Patients initiating first-line treatment for metastatic ER+/HER2- breast cancer	Time 0 will be defined as the day after the end of the 15-day exposure ascertainment window. Exposure ascertainment is described in the variables section of this protocol.	Incident	[Metastatic diagnosis date, Day -16]	Metastatic diagnosis

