7.4.3 Context and rationale for follow-up

Follow-up will begin on Day 0, and will continue until the earliest of:

1. Date of documented progression or death ([Table 7](#));
2. Initiation of any new anti-cancer therapy;
3. The administrative end of the study period (Day 1004, or 33 months, of follow-up), to align with the maximum follow-up time at which PFS was evaluated in the PALOMA-2 trial;
4. End of the data (July 20, 2023);
5. Loss to follow-up: The last date of curated EHR activity prior to a period of >90 days without curated EHR activity and without death.

Operational definitions for the study censoring criteria are presented in [Table 8](#). These censoring criteria correspond to those applied in the PALOMA-2 RCT where applicable.

Table 8. Operational Definitions of Censoring Criteria

Trial Criterion	Real-world operationalization	Rationale for real-world operationalization (where applicable)	Validity concerns and how they will be addressed (where applicable)
Initiation of a new anti-cancer treatment	Treatment with any new anti-cancer therapy.	N/A	N/A

Trial Criterion	Real-world operationalization	Rationale for real-world operationalization (where applicable)	Validity concerns and how they will be addressed (where applicable)
End of study	Administrative end of study (Day 1004, or 33 months) or July 20, 2023.	Align with maximum time in PALOMA-2 or end of available data in real-world data source.	N/A
Withdrawal of consent	This criterion is not relevant in a real-world clinical setting.	N/A	N/A
Loss to follow-up	A period of >90 days without curated EHR activity and without death.	Curated activity in the real-world data source indicates points at which progression can be recorded. Metastatic breast cancer patients likely have contact with the healthcare system at least every 90 days for lab work, prescription refills, outpatient visits, or scans. Periods greater than 90 days may indicate loss to follow-up during which censoring or outcome events cannot be captured.	Patients who use the health care system less frequently will be censored. A sensitivity analysis will be conducted expanding the period without curated activity to >180 days (Table II).

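### The Table 11 analysis for under-recorded late deaths moves the last entry date but not the end of follow-up, so it tests incomplete death capture only weakly

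*Combined protocol and SAP*

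**What the plan says.** Section 7.3.1 sets the primary entry period: "The date of first study drug initiation will be restricted to dates from February 1, 2010 to June 20, 2023". Table 3 starts the clock after exposure ascertainment: "Time 0 will be defined as the day after the end of the 15-day exposure ascertainment window".

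Section 7.4.3 ends follow-up at the first of progression or death, a new anti-cancer therapy, Day 1004, the end of data, or loss to follow-up. Table 8 gives the end-of-study rule as "Administrative end of study (Day 1004, or 33 months) or July 20, 2023". Loss to follow-up is dated at "The last date of curated EHR activity prior to a period of >90 days without curated EHR activity and without death".

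One Table 11 row (Section 7.5.2) addresses late death capture. Its rationale is "Patients identified toward the end of the available study period may not have adjudicated death data, leading to underestimates of death", and its stated strength is "Greater minimum follow-up time and opportunity for death to be identified". The only change is to the entry period, which becomes "dates at least six months before the end of the data (February 1, 2010 to February 20, 2023". The row gives no new end of follow-up, and no other section supplies one.

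**The concern.** If deaths close to the data cut have not yet been adjudicated, the gap belongs to calendar time. It affects every patient at risk in those months, whenever she entered. A woman who started in January 2022 and was still event-free in May 2023 is as exposed to an unrecorded May death as one who started in March 2023. The row drops the second and keeps the first with her follow-up unchanged.

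The loss-to-follow-up rule limits this but does not remove it. A patient with curated activity on or after April 21, 2023 cannot show a gap of more than 90 days before July 20, 2023. If she then dies unrecorded, she counts as event-free to the end of data.

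Death is part of the primary endpoint, and Section 7.6.1 says the vendor's mortality algorithm has not been validated. No other Table 11 row targets late death capture. The row with the 180-day gap lengthens the permitted silence and itself warns of more unobserved events. The risk is that agreement with the primary result is read as evidence that late deaths do not matter, when such agreement would be expected either way.

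**Working it through.** **Inputs from the documents.** End of data July 20, 2023; last entry June 20, 2023 (primary) and February 20, 2023 (sensitivity); first entry February 1, 2010; Time 0 = first study drug + 15 days; cap at Day 1004.

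**1. The plan's own intervals.**
- Primary: June 20 to July 20, 2023 = 30 days, which agrees with the stated one month (15 days from Time 0).
- Cap: 33 × 365.25 / 12 = 1,004.4 days, which agrees with Day 1004.
- Sensitivity: February 20 to July 20, 2023 = 8 + 31 + 30 + 31 + 30 + 20 = 150 days, or five months (135 days from Time 0). The stated six months does not reproduce. Six months before the end of data is January 20, 2023 (181 days).

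**2. Who can contribute follow-up in the last 181 days.**
- January 20, 2023 − 1,004 days = April 21, 2020; − 15 days = April 6, 2020. Earlier starters reach Day 1004 before the window opens.
- April 6, 2020 to June 20, 2023 = 1,170 days of entry dates.
- The row removes February 20 to June 20, 2023 = 120 days; 120 / 1,170 = 10.3%.
- A true six-month cut-off would remove January 20 to June 20, 2023 = 151 days; 151 / 1,170 = 12.9%.

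**3. Share of late person-time that stays in.** Counting entry days gives equal weight to patients who contribute unequally, so person-time is the better measure. It needs assumptions that the documents do not supply: uniform entry, and exponential exit from follow-up (all reasons combined, before the cap) with a median m of 8 to 25 months. With exit rate r = ln 2 / (30.4375 m) per day, a patient contributes (e^(−ra) − e^(−rb)) / r days to a window. Here a is the time from Time 0 to the window's opening (0 if she enters later), and b is the smaller of 1,004 and the time from Time 0 to July 20, 2023. Summing over entry dates gives:

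| Window before July 20, 2023 | Kept, last entry February 20, 2023 (as written) | Kept, last entry January 20, 2023 |
|---|---|---|
| Last 90 days | 76.6–87.1% | 69.6–82.8% |
| Last 150 days | 84.1–91.3% | 76.7–87.0% |
| Last 181 days | 86.8–92.8% | 80.5–89.1% |

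Starting the entry period in 2010 or 2015 gives the same figures, because the cap keeps all starters before April 2020 out of these windows.

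**4. The alternative.** Ending follow-up for everyone at January 20, 2023 leaves 0% of the last 181 days. With entry closed at December 20, 2022, the shortest potential follow-up is 31 days from first drug and 16 from Time 0, against 30 and 15 in the primary. A gap of more than 90 days that begins on January 20, 2023 is complete by April 21, 2023, so the loss-to-follow-up rule can be applied in full to every retained day.

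**The case against.** The strongest reply is that the row does what it says. It names patients identified late, removes those who started between February 21 and June 20, 2023, and raises the minimum potential follow-up from Time 0 from 15 to 135 days. That stands. A reader might infer that the concern is not tested at all, but the documents do not support that: early deaths among late entrants do get more time to be recorded. Late deaths among earlier entrants do not.

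A reader might also infer that everyone is followed to July 20, 2023. That is not so. Anyone who started before about October 4, 2020 reaches Day 1004 first (July 20, 2023 − 1,004 − 15 days), and the other censoring rules end follow-up earlier for many more. Nor is every unrecorded death carried to the data cut. A patient who dies 60 days before the cut, with her last activity 95 days before it, is censored at that last activity.

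A third tempting inference is that missing deaths favour palbociclib, because comparators reach back to 2010 while Table 11 places accelerated approval in 2015. This is plausible but not shown. Section 7.9 and Appendix B give arm totals, not accrual by year. Year of initiation is a candidate for the weights (Table 9), and the contemporaneous-cohort row removes pre-2015 entrants.

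Finally, this is one sensitivity analysis in a study that Section 5 says will be judged on qualitative agreement. That limits the weight of the point but does not repair the analysis.

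**Conclusion.** The point holds in a limited form. The row addresses late death capture by changing the entry date alone. It takes out about 10% of the entry dates that can feed the last six months of data and, under the stated assumptions, leaves roughly 87% to 93% of the person-time in those months. A result close to the primary would therefore say little about under-recorded deaths.

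The date arithmetic rests only on the documents. The person-time range rests on uniform entry and exponential exit. The size of any bias cannot be computed: the length of the death-data lag is not stated, accrual by arm and year is not given, and only deaths without earlier recorded progression change rwPFS. For the reasons given above, the documents do not support going further to say that the analysis tests nothing or that the bias has a known direction.

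Separately, the six-month description and the February 20, 2023 date contradict each other by one month. Correcting that date alone would still leave about 81% to 89% of the last 181 days in the analysis.

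**What to change.** In this Table 11 row, or in a new row beside it:

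- Set the administrative end of follow-up for all patients to January 20, 2023, six months before the end of data. Count progression and death only to that date. Use later records only to establish deaths up to that date and to apply the loss-to-follow-up rule.
- Close entry at December 20, 2022, one month before the new end date, as the primary rule does. Requiring only that Time 0 precede January 20, 2023 would admit patients with a single day of follow-up.
- Rewrite the description, rationale, strengths and limitations cells to match. The limitations should mention fewer events and the loss of progressions recorded after January 20, 2023. They should also say that six months is the row's own margin, not a documented lag, so a longer lag would still not be covered.
- If the entry restriction is kept as its own analysis, which preserves its longer minimum follow-up, reconcile its six-month wording with February 20, 2023 and describe it as addressing late entrants only.

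The cost is one edited or added table row and one changed censoring date, with somewhat fewer events in that analysis. The primary analysis is unchanged.
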